The primary outcome for the study is the New Mobility Score (NMS) measured at 12 months. Based on prior studies, a clinically meaningful difference in NMS of 1 point was selected, with an expected standard deviation of 2.2 points. To achieve 95% power at a 5% significance level, 127 participants are required per group. Accounting for an anticipated 30% loss to follow-up due to mortality or other causes, the target enrolment is set at 330 participants.

Framework

This study employs a superiority framework to determine whether arthroplasty provides significantly better functional outcomes than IF. Specifically, the hypothesis is that arthroplasty will result in higher NMS scores compared to IF at 12 months post-surgery.

Interim analysis and stopping guidelines

An interim analysis will be conducted after data collection from the first 70 participants, focusing on mortality and function. If a mortality difference of 10% or an NMS difference of 2 points between groups is observed at 30 days or 3 months, respectively, the trial steering committee will review whether the trial should continue. The interim analysis did not meet the set criteria's and the steering committee recommended to continue the trial.

Timing of final analysis

The final analysis will be performed after all follow-up data, including the 12-month assessments, are collected. It is estimated that the last follow-up data is collected by February 2025. Thus, the complete analysis will be conducted in spring 2025.

Timing of outcome assessments

Assessments occur at:

Baseline:	During hospital admission with demographics, comorbidity, admission, surgery, blood samples, x-rays, NMS, Pain ratings using the Verbal Rating Scale (VRS), Oxford Hip Score (OHS), and Cumulated Ambulation Score (CAS).
2 and 6 weeks:	Pain VRS, CAS at 6 weeks
3 months:	NMS, CAS, Pain VRS, OHS, EuroQol 5-Dimension 5-Level (EQ-5D-5L), Barthel-20, and the de Morton Mobility Index (DEMMI).
6 months:	NMS, Pain VRS, OHS, EQ-5D-5L, Barthel-20, and DMMI.
12 months:	NMS (primary endpoint), Pain VRS, OHS, EQ-5D-5L, Barthel-20, DMMI, reoperation rates, and mortality.

Timeframe for collection of data

	Admission	2 weeks	6 weeks	3 months	6 months	12 months	At event
Demographics	X						
Comorbidity	X						
Admission	X						
Surgery	X						
Blood	X						
X-ray	X						X
NMS	X			X	X	X	
Pain VRS	X	X	X	X	X	X	
OHS	X			X	X	X	
EQ-5D-5L	X			X	X	X	
DEMMI	X			X	X	X	
Barthel-20	X			X	X	X	
CAS	X		X	X			
Reoperation							X
Complications							X

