Verbal Rating Scale for Pain (VRS): The VRS for pain will measure patient-reported pain intensity on a scale from 0 (no pain) to 10 (worst possible pain). This outcome will be recorded at multiple time points to capture immediate and longer-term pain levels (2 weeks, 6 weeks, 3 months, 6 months, and 12 months). The Pain score is measured on a 0-10 scale. The VRS at 12 months is a secondary outcome.

Reoperation Rate: This outcome captures any surgical procedures related to implant failure or complications following the initial surgery. Reoperations will be tracked up to 12 months and will include any additional surgery required. This measure is categorical (yes/no), indicating whether a reoperation occurred within 12 months. Reoperations will be subdivided into major and minor: major is defined as any surgery that leads to the change of an implant or parts of it, removal of an implant (not simple removal of internal fixation), open reduction of a dislocated hip, operation due to periprosthetic fracture, or a DAIR (Debridement, antibiotics, and implant retention) procedure. Minor is defined as simple hardware removal of internal fixation or closed reduction of a dislocated hip.

Mortality: Mortality will be recorded as a binary outcome (alive/deceased) whenever the event occurs within the study period.

Exploratory Outcomes

These outcomes will not be included in the primary paper and consists for de Morton Mobility Index (DEMMI), Cumulated Ambulation Score, and X-ray measurements.

Analysis method

Primary Outcome Analysis

The primary outcome will be analyzed using a linear mixed-effects model to account for repeated measures across time points (baseline, 3, 6, and 12 months). The model will include fixed effects for time, and the

interaction between time and treatment, along with random intercepts for both hospital and individuals to account for within-subject correlation.

Time will be treated as a categorical variable.

$t = 0, \dots, T$ (observations time points) (fixed effect)

$i = 1, \dots, I$ (participants) (random effect as random intercept γ_i)

Treatment arm as fixed effect exposure with interaction with time

Baseline measurements will be included as time point 0.

Treatment effect at each time point

$$Y_{i,t} = b_{treatment,t} Treatment_i time_t + b_t time_t + \gamma_i + \varepsilon_{i,t}$$

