We will use an unstructured covariance structure for the random effects. If it improves model fit, time will also be added as a random effect to account for variability in NMS across time points within individuals.

Presentation: Estimated differences in NMS scores between treatment groups will be presented with β -coefficients, 95% confidence intervals (CIs), and p-values. Treatment effects will be displayed graphically across time points to illustrate trajectories by group, with error bars representing 95% CIs.

Secondary Outcome Analyses

Oxford Hip Score (OHS), EQ-5D-5L, and Verbal Rating Scale for Pain (VRS) will each be analysed using mixed-effects models as described for the primary outcome.

Reoperation Rate and Mortality: Binary outcomes (reoperation and mortality within 12 months) will be analysed using logistic regression models with treatment as a fixed effect and hospital as a random effect. Additionally, for mortality, time-to-event analysis will be conducted using Cox proportional hazards models with baseline hazards stratified by hospital.

Presentation: For secondary outcomes, results will be presented with β -coefficients, odds ratios (for binary outcomes), hazard ratios (for time-to-event mortality analysis), 95% CIs, and p-values.

[Adjustments for Covariates](#)

Analyses of the primary and secondary outcomes will be done twice, once unadjusted, and once adjusted for following covariates: Age (continuous), Sex (male/female), Comorbidity (measured by the American Society of Anesthesiologists classification).

[Assumptions Checking for Statistical Methods](#)

Linear Mixed-Effects Models: Assumptions of normality and homoscedasticity for residuals will be checked by examining quantile-quantile (Q-Q) plots and residual-vs-fitted plots.

Logistic and Cox Models: Assumptions of linearity and proportional hazards, respectively, will be assessed. The proportional hazards assumption in Cox models will be evaluated using Schoenfeld residuals. Deviations from linearity in logistic models will be reviewed by adding polynomial terms or piecewise splines as needed.

Alternative Methods if distributional assumptions do not hold

If normality assumptions are violated in the linear mixed-effects model, non-parametric bootstrapping with 1,000 replicates will be used to estimate 95% CIs for treatment effects.

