If the proportional hazards assumption is violated in the Cox regression model for mortality, we will conduct a Kaplan-Meier survival analysis. The survival curves for each treatment group will be plotted, and differences between groups will be tested using the log-rank test.

Sensitivity Analyses

Intention-to-Treat vs. Per-Protocol: The primary analysis will be conducted as intention-to-treat (ITT). A sensitivity analysis will be conducted per-protocol to assess treatment effects among participants who fully adhered to assigned interventions.

Missing Data

No missing data is expected for the Cox regression outcome (mortality and reoperation rate). For all other outcomes, mixed-effects models inherently account for missing data under the assumption that it is Missing at Random (MAR). A dropout table will be presented, summarizing the number and timing of participants lost to follow-up by treatment group.

Harms

A table summarizing all recorded harms, excluding reoperations, will be presented.

Statistical Software

All statistical analyses will be performed using Stata 18.

References

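### Reoperation is called a Cox outcome with no missing data but is analysed only as yes/no by logistic regression, with no rule for participants who withdraw or are lost before 12 months

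*SAP*

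**What the plan says.** All references are to the SAP.

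- **Section 6, Outcome definitions.** Reoperation is a secondary outcome: "Reoperations will be tracked up to 12 months and will include any additional surgery required". It is then reduced to a binary variable: "This measure is categorical (yes/no), indicating whether a reoperation occurred within 12 months".
- **Section 6, Secondary Outcome Analyses.** "Binary outcomes (reoperation and mortality within 12 months) will be analysed using logistic regression models with treatment as a fixed effect", with hospital as a random effect. The time-to-event model is added for death only: "Additionally, for mortality, time-to-event analysis will be conducted using Cox proportional hazards models with baseline hazards stratified by hospital".
- **Section 6, Missing Data.** "No missing data is expected for the Cox regression outcome (mortality and reoperation rate". All remaining outcomes are left to mixed models under missing at random. A dropout table by arm is promised.
- **Section 3, Sample size.** "Accounting for an anticipated 30% loss to follow-up due to mortality or other causes, the target enrolment is set at 330 participants".
- **Section 4, Analysis population.** The intention-to-treat set holds everyone randomised, whether or not follow-up was completed.
- **Section 5, Withdrawal/follow-up.** Withdrawals and losses are recorded with timing and reason. Participants who have data stay in the intention-to-treat analysis.
- **Section 3, Timing of outcome assessments.** The table records reoperation when the event occurs. The text list above it places reoperation rates at the 12-month assessment.

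**The concern.** Two things do not fit together.

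First, the Missing Data paragraph treats reoperation as a Cox outcome, and the analysis paragraph gives it no Cox model. The difference has consequences. A Cox model can use a participant observed for two months as two months of follow-up. A logistic model for a 12-month yes/no cannot.

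Second, reoperation is exempted from any missing-data rule on the expectation that nothing will be missing, in a trial that plans for withdrawal and loss. For a participant who withdraws at month 2 without a reoperation, the population definition in Section 4 points to keeping the person, in practice as a no. The wording in Section 5 allows leaving the person out. The two codings give different denominators and different odds ratios, and the SAP does not choose. It also names no source of reoperation events that continues after withdrawal.

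At stake are the reported 12-month reoperation rate in each arm and a clear meaning for the odds ratio. Reoperation is a named secondary outcome, and the SAP's own background reports conflicting earlier results on it.

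**Working it through.** The SAP gives no reoperation rate and no reoperation power, so there is no stated reoperation figure to reproduce. The 30% can be traced to its use.

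1. **Where the 30% belongs.** For NMS, a difference of 1 point, SD 2.2, two-sided 5% and 95% power: n = 2 × (1.960 + 1.645)² × 2.2² / 1² ≈ 126 per group, against 127 stated. Then 2 × 127 = 254 and 254 × 1.3 = 330.2, the stated 330. The 30% is therefore an allowance for the visit-based NMS. It pools death with other causes and gives no split. (Dividing by 0.7 would give 363. That is a separate matter and does not bear on this point.)

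2. **Assumptions for the illustration.** The 12-month reoperation risk without any loss is r = 10%, with constant hazard l = −ln(1 − r) = 0.1054. Loss is independent of reoperation. Reoperations after withdrawal are not seen, and the person is coded no.

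3. **All losses are withdrawals, spread uniformly over the year.** Recorded risk = (1 − L) × r + L × [1 − (1 − e^(−l))/l]. The bracket is 1 − 0.10/0.1054 = 0.0509.
   - L = 30%: 0.70 × 0.10 + 0.30 × 0.0509 = 0.0853, a relative understatement of about 15%.
   - L = 15%: 0.85 × 0.10 + 0.15 × 0.0509 = 0.0926, about 7%.
   - With r = 5% and L = 30% the recorded risk is 0.0426, again about 15%.

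4. **Losses split between death and withdrawal.** Use constant hazards d (death) and w (withdrawal), with d + w = −ln(0.70) = 0.3567 divided in proportion to the split. The true share reoperated is l/(l + d) × (1 − e^(−(l + d))). The counted share is l/(l + d + w) × (1 − e^(−(l + d + w))) = 0.1054/0.4620 × (1 − 0.63) = 0.0844 for every split.

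| Deaths / withdrawals | True share reoperated | Counted share | Relative understatement |
|---|---|---|---|
| 30% / 0% | 8.4% | 8.4% | 0 |
| 20% / 10% | 8.9% | 8.4% | about 5% |
| 15% / 15% | 9.2% | 8.4% | about 8% |
| 0% / 30% | 10.0% | 8.4% | about 16% |

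The last row differs slightly from step 3 (8.4% against 8.5%) only because loss follows a constant hazard here instead of a uniform pattern. For assumed risks of 5% to 20% the largest relative figure stays at about 15% to 16%, at most 3.1 percentage points.

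5. **The other possible coding.** Suppose withdrawn participants without a reoperation are dropped, while those reoperated before withdrawal are kept. In the extreme case of step 3, the share dropped is 0.30 × (1 − 0.0509) = 0.2847, and the recorded rate is 0.0853 / (1 − 0.2847) = 0.119. The unstated coding thus decides even the sign of the error in the absolute rate.

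**The case against.** The strongest reply has four parts.

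- **Deaths.** A reader might infer that people who die early are wrongly counted as successes and that this understates the rate. It does not. With all randomised in the denominator, a death before reoperation counted as a no gives exactly the cumulative incidence with death as a competing event. The figure is lower only than a hypothetical risk with death removed, which the SAP does not set out to estimate. This part stands in full. A difference in mortality between arms would still affect how the odds ratio is read.
- **No rule is written.** A reader might infer that the SAP orders withdrawn participants to be coded no. It does not. Expecting no missing data may simply mean that ascertainment is expected to be complete, and recording at event is compatible with that. If events are captured after withdrawal, nothing is missing. The source of events may also be described in the protocol, which is not at hand. This stands as a possibility, but the SAP does not confirm it, and its text list ties reoperation to the 12-month assessment.
- **The 30% is not missing reoperation status.** Correct: it was set for NMS and includes deaths, so it serves only as an upper bound.
- **Bias between arms is speculative.** Also correct. The SAP gives no loss by arm. Even an invented split of 35% against 25% moves a 10% risk to 8.3% and 8.8%, a ratio of 0.94. With 165 per arm the standard error of the log risk ratio is about √(2 × 0.9 / 16.5) = 0.33, so that shift is about 0.17 standard errors. If the excess losses were deaths, 0.94 would be the real ratio of cumulative incidences.

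A 12-month binary outcome with logistic regression is a legitimate choice when status is known for everyone. What remains is that the SAP neither shows this nor says what happens otherwise.

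**Conclusion.** The point holds in a limited form. The text contradicts itself on the model for reoperation. It also leaves reoperation without a rule for follow-up that ends early for reasons other than death, while expecting such losses.

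The effect on the absolute rate, if withdrawn participants are counted as reoperation-free, lies between 0 and about 15% relative (10% recorded as 8.5%). It is 0 if capture is complete or all losses are deaths. The upper end needs all 30% to be withdrawals with later events unseen. These figures rest on an assumed 10% risk, constant reoperation hazard, uniform loss and independence of loss and reoperation. If reoperations cluster early, the effect is smaller.

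The SAP does not support the inference that one arm is favoured, and its background does not say that reoperation is where the treatments differ most. The matter is modest in size but should be settled before unblinding, because the coding is otherwise chosen with the data in view.

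**What to change.** Reconcile the Missing Data and Secondary Outcome Analyses paragraphs of Section 6 as follows.

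- Analyse time from index surgery to first reoperation, with death as a competing event and follow-up ending at 12 months. Censor at withdrawal or last contact only where reoperations are not captured afterwards.
- State the source of reoperation events and whether it continues after withdrawal.
- Report the 12-month cumulative incidence per arm with 95% CI, using an estimator that handles the competing event (Aalen–Johansen, not one minus Kaplan–Meier). Add a cause-specific hazard ratio from a Cox model stratified by hospital, as already planned for mortality.
- Keep the logistic odds ratio as supportive, with the coding of participants without 12 months of observation written down.
- Replace the expectation of no missing reoperation data with this censoring rule, and note that it assumes withdrawal is independent of reoperation risk.

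The cost is a few sentences in the SAP and a few lines of code. Reoperation and death are already recorded at event, and withdrawal with its timing. The downside is one more estimate to report. Compared with coding everyone without a recorded reoperation as a no, the rates change only through the withdrawals; the handling of deaths stays as it is.
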